7.8.3 Vital signs

The analyses of vital signs (blood pressure and pulse rate) will be descriptive in nature. Descriptive statistics of vital signs over time and for the difference from baseline (see [Section 6.7](#)) will be provided.

Clinically relevant findings in vital signs data will be reported as baseline conditions (prior to first administration of study treatment) or as AEs (after first administration of study treatment) if judged clinically relevant by the investigator, and will be analyzed as such.

7.8.4 ECG

Relevant ECG findings will be reported as relevant medical history/baseline condition (if a condition already exists before first administration of study treatment) or as AE (if condition emerges after first administration of study treatment) and will be summarized as such. No separate listing or analysis of ECG findings will be prepared.

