5.2.4.2 Continuous ECG monitoring

Cardiac rhythm (including heart rate) will be monitored by means of continuous 12-lead ECG recording at visit 2 for at least 15 min before CCK-4 challenge until 30 min after the challenge and at visit 3 and 4 for at least 2 h before the BI 1358894 administration (for baseline assessment), and 6 h following drug administration using patient monitors (e.g. Mortara Telemetry System). Abnormal findings will be recorded as AEs if judged clinically relevant by the Investigator but no other data will be transferred to the database.

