5.2.6 Assessment of adverse events

5.2.6.1 Definitions of adverse events

5.2.6.1.1 Adverse event

An adverse event (AE) is defined as any untoward medical occurrence in a patient or clinical investigation subject administered a medicinal product and which does not necessarily have to have a causal relationship with this treatment.

An AE can therefore be any unfavourable and unintended sign (including an abnormal laboratory finding), symptom, or disease temporally associated with the use of a medicinal product, whether or not considered related to the medicinal product.

The following should also be recorded as an AE in the CRF and BI SAE form (if applicable):

- Worsening of the underlying disease or of other pre-existing conditions
- Changes in vital signs, ECG, physical examination, and laboratory test results, if they are judged clinically relevant by the investigator

If such abnormalities already pre-exist prior to trial inclusion, they will be considered as baseline conditions and should be collected in the eCRF only.

The provoked panic symptoms in response to CCK-4 injection (as documented by the PSS score), which are prerequisite for demonstrating a potential effect of the investigational compound, will be considered PD parameters. Since they are an expected and desired response in the context of this trial (even though they constitute an untoward medical occurrence), they will not be recorded as AEs. All other observations not included on the PSS questionnaire occurring during the standard AE reporting time period (see [Section 5.2.6.2.1](#)) are to be documented as AEs.

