5.2.6.2 Adverse event collection and reporting

5.2.6.2.1 AE collection

Upon enrolment into a trial, the subject's baseline condition is assessed (for instance, by documentation of medical history/concomitant diagnoses), and relevant changes from baseline are noted subsequently.

Subjects will be required to report spontaneously any AEs as well as the time of onset, end time, and intensity of these events. In addition, each subject will be regularly assessed by the medical staff throughout the clinical trial and whenever the investigator deems necessary. As a minimum, subjects will be questioned for AEs (and concomitant therapies) at the time points indicated in the [Flow Chart](#). Assessment will be made using non-specific questions such as 'How do you feel?'. Specific questions will be asked wherever necessary in order to more precisely describe an AE.

A carefully written record of all AEs shall be kept by the investigator in charge of the trial. Records of AEs shall include data on the time of onset, end time, intensity of the event, and any treatment or action required for the event and its outcome.

The following must be collected and documented on the appropriate CRF(s) by the investigator:

- From signing the informed consent onwards until an individual subject's end of trial:

Proprietary confidential information © 2019 Boehringer Ingelheim International GmbH or one or more of its affiliated companies

- All AEs (serious and non-serious) and all AESIs
- The only exception to this rule are AEs (serious and non-serious) and AESIs in Phase I trials in healthy volunteers, when subjects discontinue from the trial due to screening failures prior to administration of any trial medication. In these cases, the subjects' data must be collected at trial site but will not be entered in the CRF or trial database and will not be reported in the CTR.
- After the individual subject's end of trial:
 - The investigator does not need to actively monitor the subject for AEs but should only report any occurrence of cancer and related SAEs and related AESIs of which the investigator may become aware of by any means of communication, e.g. phone call. Those AEs should, however, not be reported in the CRF.

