6.2 DETAILS OF TRIAL PROCEDURES AT SELECTED VISITS

6.2.1 Screening periods

In Screening Visit 1, after having been informed about the trial, all subjects will provide written informed consent in accordance with GCP and local legislation prior to enrolment in the study.

For information regarding laboratory tests (including drug and virus screening), ECG, vital signs, and physical examination, refer to [Sections 5.2.3 to 5.2.5](#).

In Screening Visit 2 (on one day between Days -6 and -2), subjects will undergo a CCK-4 challenge test. Only subjects with sufficient CCK-4 sensitivity (see [Section 3.3](#)) will enter the treatment periods.

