Possibly clinically significant abnormal laboratory values are only those identified either in the Investigator's comments or at the Report Planning Meeting at the latest. It is the Investigator's responsibility to decide whether a lab value is clinically significant abnormal or not. Standard or project-specific rules for flagging clinically significant values in an automated manner will not be applied in this study.

Clinically relevant findings in laboratory data will be reported as baseline conditions (prior to first administration of study treatment) or as AEs (after first administration of study treatment) if judged clinically relevant by the investigator, and will be analyzed as such.

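### SAP 7.8.2 to 7.8.4 draw the baseline/AE line at the first BI 1358894 or placebo dose, after every treated subject has already had CCK-4, against the protocol and the SAP's own Screening AE phase

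*SAP*

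**What the plan says.** **SAP.** Section 7.8.4 reads "Relevant ECG findings will be reported as relevant medical history/baseline condition (if a condition already exists before first administration of study treatment"), and makes a finding an AE if it emerges afterwards. It plans no separate ECG listing or analysis. For laboratory data, 7.8.2 reads "Clinically relevant findings in laboratory data will be reported as baseline conditions (prior to first administration of study treatment"), and 7.8.3 reads "Clinically relevant findings in vital signs data will be reported as baseline conditions (prior to first administration of study treatment"). Sections 7.8.5.1 and 7.8.5.2 use the ECG wording for physical and neurological findings. Table 6.1:1 defines a Screening AE phase from informed consent to the first BI 1358894 or placebo dose, and 7.8.1 assigns AEs to it.

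**Protocol.** Section 6.2.1: "In Screening Visit 2 (on one day between Days -6 and -2), subjects will undergo a CCK-4 challenge test". Section 5.2.4.2 has continuous ECG running at Visit 2 from before the challenge until 30 minutes after it, and says: "Abnormal findings will be recorded as AEs if judged clinically relevant by the Investigator". Section 5.2.6.2.1 sets the window for collecting AEs: "From signing the informed consent onwards until an individual subject's end of trial". Section 5.2.6.1.1 says of abnormalities: "If such abnormalities already pre-exist prior to trial inclusion, they will be considered as baseline conditions".

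**The concern.** The SAP's dividing line would suit a trial in which nothing pharmacologically active is given before the first dose. Here a provoking agent is given two to six days earlier, and protocol 1.2.2 and 1.4.2.2 expect it to change blood pressure and pulse. On the SAP wording, a new clinically relevant finding after the screening injection is a baseline condition, while the same finding after the injection in a treatment period is an AE. The stake is the completeness of the AE record for the first CCK-4 exposure in treated subjects. SAP Section 4 lists only changes to the analysis sets, so this difference from the protocol is not declared as one.

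**Working it through.** No plan figure has to be reproduced. The check sets the classification rules side by side.

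1. **Meaning of study treatment.** The SAP does not define the term. Section 6.1 lists CCK-4 apart from the two investigational treatments, as non-investigational. Table 6.1:1 starts the on-treatment phase at BI 1358894 or placebo, and 6.3 narrows the treated set to investigational study drug. I therefore read the line as the first BI 1358894 or placebo dose.

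2. **Exposure before that line.** Exclusion criterion 26 (protocol 3.3.3) bars subjects who respond insufficiently to CCK-4 at Visit 2. Every subject correctly entered has therefore had the injection.

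3. **One test case.** Take a clinically relevant finding that is new after the Visit 2 injection, in a subject who goes on to be treated:

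| Rule | Dividing line | Class |
|---|---|---|
| SAP 7.8.2, 7.8.3 | first study treatment | baseline condition |
| SAP 7.8.4 | first study treatment | medical history/baseline condition |
| SAP 6.1 (Table 6.1:1), 7.8.1 | Screening phase runs from consent to first dose | Screening-phase AE |
| Protocol 5.2.4.2 (continuous ECG) | none; Visit 2 is covered | AE |
| Protocol 5.2.6.2.1 | consent | AE |
| Protocol 5.2.6.1.1 | trial inclusion | AE, if inclusion means consent |
| Protocol 7.3.4 | first intake | AEs before it go to the screening period; relevant ECG findings are AEs |
| Protocol 5.2.4.1 (12-lead ECG) | at screening or during the trial | baseline condition |

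SAP 7.8.2 to 7.8.4 agree with only one other row, protocol 5.2.4.1, and that row covers 12-lead recordings only.

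4. **Continuous ECG.** Protocol 5.2.4.2 sends nothing from this recording to the database except relevant findings entered as AEs, and SAP 7.8.4 plans no ECG listing. If the SAP rule takes a Visit 2 finding out of the AEs, the only record the protocol plans from that recording is gone.

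5. **Count.** Protocol 4.1.1 gives 3 CCK-4 doses per subject, and 7.7 plans 20 subjects. If all complete both periods, 20 × 3 = 60 injections. Of these, 20 × 1 = 20 fall before the line and 20 × 2 = 40 after it, and 20/60 is one third. The documents give no frequency of clinically relevant findings after CCK-4, so the number of findings affected cannot be estimated.

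**The case against.** A reader might infer that reactions to the screening challenge in general become medical history. The documents do not support that:
- Events entered as AEs keep the Screening phase. They are displayed in CTR Appendix 16.1.13.1.8.1, with a total over screening and on-treatment.
- Local reactions are summarised over all injections (SAP 5.3.3).
- Panic symptoms on the PSS are PD data and are not AEs in any period (protocol 5.2.6.1.1).
- For laboratory and vital signs the SAP speaks of baseline conditions only, not history.

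Nor can one infer that every laboratory, vital-sign, ECG, physical and neurological finding after the 20 screening injections is affected. Only new or worsened, clinically relevant findings are in question. The Flow Chart footnotes place no physical or neurological examination between the Visit 2 injection and the first dose. Many relevant findings would make the subject ineligible (exclusion criteria 1, 4 and 21), and data of screening failures do not enter the CRF.

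A reader might also infer that the causality assessment is compromised. That is not shown. The investigator judges causality with relevant history and re-challenge in view (protocol 5.2.6.1.8), and a baseline entry remains available for that.

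Three further points have some force:
- The protocol governs what the investigator records, and nothing in SAP 7.8 orders a recorded AE to be reclassified. However, two rules then give one finding different classes, and the SAP does not say which prevails.
- CCK-4 effects are described as lasting about 5 minutes, so an event that has resolved arguably does not already exist at first dose. That may take it out of the ECG wording, but it leaves it unclassified there, and 7.8.2 and 7.8.3 carry no such limit.
- Trial inclusion is not defined. If it means meeting all entry criteria, it falls after Visit 2 and 5.2.6.1.1 no longer conflicts. Sections 5.2.4.2 and 5.2.6.2.1 still do.

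**Conclusion.** The point holds as an inconsistency in how laboratory, vital-sign and ECG findings between the Visit 2 injection and the first dose are classified. It is firmest for continuous ECG, where the protocol is explicit and no other data are kept. For 12-lead ECG the SAP follows protocol 5.2.4.1, so the conflict there lies partly within the protocol. For physical and neurological findings it matters only for consistency, since no examination is scheduled in that interval.

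The size is bounded by exposure: one of each treated subject's three CCK-4 injections precedes the line. The number of findings affected is unknown and may well be small. The conclusion assumes that study treatment means BI 1358894 or placebo. The part resting on 5.2.6.1.1 also assumes that trial inclusion means enrolment by consent, the sense in which protocol 3.3 uses enrolled. The primary endpoint and the on-treatment AE tables are not touched. The change is worth making because it costs almost nothing.

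**What to change.** In SAP 7.8.2, 7.8.3 and 7.8.4, and for consistency in 7.8.5.1 and 7.8.5.2, state two things:
- A clinically relevant finding that first appears or worsens after trial inclusion, including after the Visit 2 CCK-4 injection, and before the first BI 1358894 or placebo dose is analysed as an AE in the Screening phase of Table 6.1:1.
- Only conditions that pre-exist trial inclusion are baseline conditions or medical history.

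Say that trial inclusion means signing of informed consent, so that the line matches the start of AE collection. Reconcile protocol 5.2.4.1 with 5.2.4.2 and 5.2.6.1.1, so that 12-lead and continuous recordings follow one rule, and add a matching CRF instruction.

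No new data are needed. The Screening-phase count in the CTR appendix, and the total there that includes it, may rise slightly. CTR Section 15 shows on-treatment AEs only and stays as planned.

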7.8.5 Others

7.8.5.1 Physical examination

Physical examination findings will be reported as relevant medical history/baseline condition (if a condition already exists before first administration of study treatment) or as AE (if condition emerges after first administration of study treatment) and will be summarized as such. No separate listing or analysis of physical examination findings will be prepared.

7.8.5.2 Neurological examination

Clinically relevant findings of the neurological examination will be reported as relevant medical history/baseline condition (if a condition already exists before first administration of study treatment) or as AE (if condition emerges after first administration of study treatment) and will be summarized as such. No separate listing or analysis of neurological examinations will be prepared.

7.8.5.3 Suicidality assessment

Suicidality monitoring will be performed as described in Section 5.2.2 of the CTP, results will only be listed: No further analysis will be prepared.

8. REFERENCES

10. HISTORY TABLE

Table 10: 1 History table

Version	Date (DD-MMM-YY)	Author	Sections changed	Brief description of change
Final	29-AUG-2019		None	This is the final TSAP
